3.2.2. Secondary Exploratory Endpoints

- Proportion of patients with symptomatic remission at Week 6, defined by the Mayo sub scores, i) rectal bleeding of 0, ii) stool frequency of 0 or 1 (with at least one point decrease from Baseline, Week 0), (patient reported outcome) [PRO2]
- Proportion of patients with absence of rectal bleeding at Week 6, defined by the Mayo sub score rectal bleeding of 0
- Proportion of patients with normal or enhanced stool frequency at Week 6, defined by the Mayo sub score stool frequency of 0 or 1 (with at least one point decrease from Baseline, Week 0)
- Proportion of patients with endoscopic remission at Week 6, defined by the Modified Mayo endoscopic sub score of 0 or 1 (excluding friability)
- Proportion of patients with histological remission at Week 6, defined by the Nancy histological index of grade 0 or 1
- Proportion of patients with complete histological remission at Week 6, defined by the Nancy histological index [\[17,18\]](#) grade of 0
- Proportion of patients with histological response at Week 6, defined by the Nancy histological index score of ≤ 2 (if 2 then with at least one point decrease from Baseline, Week 0)
- Proportion of patients with endoscopic and histological remission at Week 6
- Proportion of patients with symptomatic remission at Week 4, defined by the Mayo sub scores, i) rectal bleeding of 0, ii) stool frequency of 0 or 1 (with at least one point decrease from Baseline, Week 0), (patient reported outcome) [PRO2]
- Proportion of patients with absence of rectal bleeding at Week 4, defined by the Mayo sub score rectal bleeding of 0
- Proportion of patients with normal or enhanced stool frequency at Week 4, defined by the Mayo sub score stool frequency of 0 or 1 (with at least one point decrease from Baseline, Week 0)
- Proportion of patients with modified clinical remission at Week 6, defined by the Modified Mayo score ≤ 2 and sub scores, i) rectal bleeding of 0, ii) stool frequency of 0 or 1 (with at least one point decrease from Baseline, Week 0), iii) endoscopy score of 0 or 1 (excluding friability) and iiiii) physician's global assessment (PGA) of 0 or 1

- Proportion of patients with durable symptomatic remission, defined by the Mayo sub scores, i) rectal bleeding of 0, ii) stool frequency of 0 or 1 (with at least one point decrease from Baseline, Week 0) [PRO2] at both Week 6 and Week 10

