- Proportion of patients with clinical response at Week 6, defined as clinical remission or a three point and ≥ 30 % decrease from Baseline, Week 0 in the sum of the Modified Mayo score, i) rectal bleeding, ii) stool frequency and iii) endoscopy score (excluding friability), iiiii) physicians global assessment (PGA)
- Proportion of patients with a defecation urgency score of 0 or a decrease of at least one point in defecation urgency at Week 6 compared to Baseline, Week 0
- Mean change in faecal calprotectin at Week 1, 2, 3, and 6 compared to Baseline, Week 0
- Mean change in steroid dosage for patients in remission at Week 6 to Week 10
- Mean change in each of the inflammatory bowel disease questionnaire (IBDQ) sub domains at Week 6 compared to Baseline, Week 0

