4.1. Inclusion Criteria

Patients must meet all of the following inclusion criteria to be randomised in the study:

1. Male or female ≥ 18 years of age
2. Established diagnosis of UC, with minimum time from diagnosis of ≥ 3 months
3. Moderately to severely active left sided UC (disease should extend 15 cm or more above the anal verge and not beyond the splenic flexure) determined by

a Modified Mayo score (excluding the friability at grade 1 for the endoscopic sub score) of 6 to 12 with an endoscopic sub score ≥ 2 assessed by central reading of endoscopy performed at screening visit 1b, and no other individual sub score < 1

4. Current oral 5-ASA/SP use or a history of oral 5-ASA/SP use
5. Current GCS use or history of GCS dependency, refractory, or intolerance, including no GCS treatment due to earlier side-effects (only one of the GCS criteria have to be fulfilled, see definition in European Crohn's and Colitis organisation (ECCO) guidelines)
6. Demonstrated an inadequate response, loss of response, or intolerance to **at least one** of the following agents:
 - Immunomodulators, e.g. cyclosporine, methotrexate, AZA/6-MP, tacrolimus
 - For example, signs and symptoms of persistently active disease despite previous treatment with at least one 8 week regimen of oral AZA (≥ 1.5 mg/kg) or 6-MP (≥ 0.75 mg/kg) or lower doses prompted by intolerance or thiopurine methyltransferase (TPMT) deficiency *or*
 - For example, previous intolerance (including, but not limited to, nausea/vomiting, abdominal pain, pancreatitis, liver function test (LFT) abnormalities, lymphopenia, TPMT genetic mutation, infection) to at least one immunomodulator
 - TNF- α inhibitors and/or anti-integrins:
 - Signs and symptoms of persistently active disease despite previous treatment with at least one induction regimen with 2 doses at least 2 weeks apart (or doses as recommended according to the current labels) of for e.g.:
 - Infliximab 5 mg/kg (intravenous (IV)) *or*
 - Golimumab 200/100 mg (subcutaneous (SC)) *or*
 - Adalimumab 160/80 mg (SC) *or*
 - Vedolizumab 300 mg (IV) *or*
 - History of intolerance (including but not limited to infusion-related reaction, demyelination, congestive heart failure, infection)

Recurrence of symptoms during maintenance dosing with any of the above medications following prior clinical benefit, (secondary failure) [discontinuation despite clinical benefit does not qualify]

7. Allowed to receive a therapeutic dose of following UC drugs during the study:

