5.7. Concomitant Medications

All medications that the patient is prescribed and has taken during the study must be recorded in the eCRF. Any changes need to be reported.

The following concomitant UC medications are allowed:

- Oral GCS therapy (≤ 20 mg prednisone or equivalent/daily) providing that the dose has been stable for 2 weeks prior to visit 1a, and need to be kept stable up to primary endpoint (Week 6). Tapering can start at Week 6 if patients are in remission, see suggested tapering scheme below.
- Oral MMX Budesonide therapy (9mg/daily) initiated at least 8 weeks before screening visit 1 a and need to be kept stable up to primary endpoint (Week 6). Tapering can start at Week 6 if patients are in remission. Tapering per local practice.
- Oral 5-ASA and/or SP compounds, providing that the dose has been stable for 2 weeks prior to visit 1a, and initiated at least 8 weeks before visit 1a. Stable dose up to end of study (Week 10).
- AZA/6-MP providing that the dose has been stable for 8 weeks prior to visit 1b, and been initiated at least 3 months before visit 1a. Stable dose up to end of study (Week 10).

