5.9. Oral Corticosteroid Tapering Regimen

Steroid tapering is recommended to start when the patient has reached clinical remission, but earliest at Week 6. Once the decision to initiate steroid tapering is taken based on the investigator's assessment, reduction of the oral steroid dosage following the schedule outlined in the table below is recommended (Table 2). Consideration of the risk of adrenal gland insufficiency is cautioned, especially when the daily dose is lowered to less than 10 mg. For patient who cannot tolerate the corticosteroid taper without recurrence of clinical symptoms the dose may be increased up to original dose. For oral MMX budesonide the tapering schedule should follow the local practice.

Table 2. Schedule of Oral Steroid Dose Reduction given in Mg/Day.

Week	Starting steroid dose		
	20 mg/day	15 mg/day	10 mg/day
6-7	15	10	7.5
7-8	10	7.5	5
8-9	7.5	5	2.5
9-10	5	2.5	0
10-11	2.5	0	0
11-12	0	0	0

Final visit in the study is Week 10, table show titration after study completion as a guide

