7.14. Mayo Score

- Full Mayo Score

A full Mayo score includes the sub scores; stool frequency, rectal bleeding, endoscopy and PGA.

- Modified Mayo Score

The Modified Mayo Score excludes the friability at grade 1 for the endoscopic sub score.

The Modified Mayo Score excluding friability at grade 1 ([appendix 15.1](#)), [21] will be used at visit 2b, to evaluate eligibility to the study.

The sub scores stool frequency and blood in stool will be evaluated during screening period, using eDiary data for the sub scores. The endoscopy sub score will be assessed by using centrally read result from a full colonoscopy (performed within 10 days prior Visit 2b) or sigmoidoscopy (at Visit 6).

- Patient Reported Outcome

PRO2 includes the sub score; stool frequency and rectal bleeding reported daily by the patient and via an eDiary.

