9.6. Exploratory Efficacy Endpoints Analyses

No multiplicity adjustments are made computing p-values of tests on exploratory variables; reported p-values are nominal. For overall comparison among more than two groups, the null hypothesis is that the proportions are the same in all groups.

The same analysis approach used for the primary efficacy endpoint will be applied to the exploratory efficacy variables referred to as a “Proportion endpoints”.

Continuous endpoints such as mean change from baseline will be evaluated using the ANCOVA, including treatment and stratifying factors as fixed factors and baseline as a covariate in the model.

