9.8. Adjustment of Covariates

Baseline values of the parameters to be analysed will be used as covariates in exploratory analyses. In addition, the prior use of TNF- α inhibitor and GCS use will be included as a covariate in exploratory analyses.

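### The exploratory steroid-dose endpoint covers only Week 6 remitters, so a between-arm test of it would not compare randomised groups; report it descriptively (minor)

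*Combined protocol and SAP*

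**What the plan says.** The endpoint appears in the synopsis and in section 3.2.2 as "Mean change in steroid dosage for patients in remission at Week 6 to Week 10". The bullet names no remission definition and no comparison with placebo. The same section uses several kinds of remission, for example "Proportion of patients with modified clinical remission at Week 6", alongside symptomatic, endoscopic and histological remission; section 3.2.1 defines clinical remission for the primary endpoint.

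On tapering, section 5.9 says "Steroid tapering is recommended to start when the patient has reached clinical remission, but earliest at Week 6" and leaves the decision to the investigator's assessment. Section 5.7 says "Tapering can start at Week 6 if patients are in remission, see suggested tapering scheme below", with no qualifier on remission. For the Mayo score, section 7.14 says "The endoscopy sub score will be assessed by using centrally read result".

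On analysis, section 9.6 says "Continuous endpoints such as mean change from baseline will be evaluated using the ANCOVA", with treatment and the stratification factors as fixed factors and baseline as covariate, and it calls reported p-values nominal. Section 9.8 adds that "GCS use will be included as a covariate in exploratory analyses". Neither section exempts the steroid endpoint. Section 9.5 treats all results as exploratory, and section 9.1 leaves technical detail to a separate SAP.

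Not every patient takes steroids. The entry criterion in section 4.1 is "Current GCS use or history of GCS dependency, refractory, or intolerance", so a history is enough.

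**The concern.** Remission is the outcome that cobitolimod is meant to produce. If it works, the active remitters include patients who would not have remitted on placebo, while the placebo remitters do not. The two sets can then differ in prognosis and in how well they tolerate a taper, whatever the drug does to steroid need. Stratification and baseline covariates do not restore the balance that randomisation gave.

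The restriction also removes the main route by which the drug could lower steroid use, which is that more patients reach remission and start to taper. At stake is one exploratory result: a p-value among remitters could be read as evidence for or against steroid sparing when it supports neither.

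**Working it through.** **Plan's own figure.** Section 9.2 uses 10% vs 35%, one-sided 0.10 and 90% power. With a pooled-variance chi-square, n = [1.2816 × √(2 × 0.225 × 0.775) + 1.2816 × √(0.10 × 0.90 + 0.35 × 0.65)]² / 0.25² = (0.757 + 0.722)² / 0.0625 = 35.0. The stated 35 per group reproduces. At 43 per arm, two-sided 0.05, power is 0.804, as claimed.

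**Expected remitters**, taking remission as the primary endpoint: placebo 43 × 0.10 = 4.3; each active arm 43 × 0.35 = 15.05.

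**Remitters on steroids.** The share on glucocorticosteroids (GCS) is not stated, so a range is assumed. The last column is the Binomial(43, 0.10 × share) probability.

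| Assumed GCS share | Placebo | Per active arm | Chance of one or none on placebo |
|---|---|---|---|
| 30% | 1.3 | 4.5 | 63% |
| 50% | 2.2 | 7.5 | 36% |
| 70% | 3.0 | 10.5 | 19% |

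**Precision, best case** (every remitter on steroids, two-arm comparison): 95% half-width = t(0.975; 17.35 df) × √(1/4.3 + 1/15.05) = 2.107 × 0.547 = 1.15 SD. Pooling residual variance over five arms gives about 1.10 SD.

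**Direction of bias, illustration only.** Assumptions:
- All start at 20 mg. A patient who holds the taper is on 5 mg in the Week 9-10 row of Table 2 (change -15 mg); otherwise the change is 0.
- 10% of patients would remit on either arm and 25% only on drug. Their chances of holding the taper are hA and hD.
- The drug itself does not affect holding.

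The active remitters' hold rate is (0.10 hA + 0.25 hD) / 0.35; the placebo remitters' is hA. The remitters-only difference is -15 × (active rate - hA). The whole-stratum difference is -15 × 0.25 hD.

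| hA / hD | Active hold rate | Remitters only, active minus placebo | Whole GCS stratum |
|---|---|---|---|
| 90% / 50% | 0.614 | +4.3 mg | -1.9 mg |
| 90% / 70% | 0.757 | +2.1 mg | -2.6 mg |
| 80% / 80% | 0.800 | 0 | -3.0 mg |
| 70% / 90% | 0.843 | -2.1 mg | -3.4 mg |

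**Power of a whole-stratum comparison** (50% GCS share, so 21.5 per arm; 80% hold in both groups; normal approximation). Placebo tapers with probability 0.10 × 0.8 = 0.08, active with 0.35 × 0.8 = 0.28. SE = 15 × √[(0.08 × 0.92 + 0.28 × 0.72) / 21.5] = 1.70 mg. Difference / SE = 3.0 / 1.70 = 1.77.
- No dropout or rescue: power 0.69 at one-sided 0.10, 0.42 at two-sided 0.05.
- 20% dropout (17.2 per arm): 0.62 and 0.35.
- If instead 10-30% of non-remitters rise by 20 mg (assumed): 0.55-0.52 at one-sided 0.10.

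**The case against.** - **The test is inferred.** Section 9.6 speaks of change from baseline. The calprotectin and quality-of-life bullets name Week 0 as their reference; the steroid bullet does not. A reader might infer that the protocol commits to a p-value. It does not: the bullet names no placebo comparison and the separate SAP could make the endpoint descriptive. What stands is that section 9.6 gives the only rule for continuous endpoints and nothing sets this one apart.
- **Remission is not undefined.** A reader might infer that it is. Section 5.9 ties tapering to clinical remission and section 3.2.1 defines that at Week 6, so the intended meaning is reasonably clear. The bullet only fails to name it. Because the investigator decides on tapering while the endpoint uses central reading, tapering patients and clinical remitters need not coincide.
- **The interval is clear enough.** Doses are held stable to Week 6, tapering starts no earlier, and no endoscopy is scheduled at Week 10. A dose change from Week 6 to Week 10 is the evident reading.
- **The restriction follows the design.** Only remitters are expected to taper, and no stated objective mentions steroid sparing. As a description of how tapering went, the endpoint is reasonable. This argues for descriptive reporting, not for a test.
- **The alternative adds little.** In the model above, the whole-stratum effect is the remission difference rescaled. That is fair, and it is why the comparison is offered as optional.

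**Conclusion.** The point holds in a limited form and is minor. The endpoint is conditioned on a post-randomisation outcome, and the general analysis rule would most likely attach a treatment comparison to it. That comparison would not be between randomised groups under any of the protocol's remission definitions. It would also be very imprecise, with about 4.3 placebo remitters at planning rates and fewer on steroids.

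A reader might infer from the illustration that the result would have the wrong sign. The documents do not support that. The sign rests wholly on assumed hold rates: the remitters-only contrast runs from +4.3 to -2.1 mg and is zero when the two groups hold equally well. The GCS shares, the 20 mg start and the all-or-nothing taper are also assumptions.

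Nor does the point reach the primary analysis or the sample size, both of which are unaffected.

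**What to change.** 1. In section 3.2.2 and the synopsis, name the remission definition (clinical remission as in section 3.2.1, if that is meant, which agrees with section 5.9). Give the dose interval as Week 6 to Week 10, and say whether remitters not on steroids are included.
2. In section 9.6 or the SAP, state that this endpoint is summarised descriptively by arm, with no between-arm p-value.
3. Only if a between-arm steroid comparison is wanted: analyse the change in recorded dose from Week 0 to Week 10 in all full-analysis-set patients in the GCS = Yes randomisation stratum, regardless of remission. Use ANCOVA with baseline dose and prior TNF inhibitor use (GCS use is constant there), count recorded increases, and report the estimate with its confidence interval.

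Items 1 and 2 are wording changes. Item 3 uses the stratum from section 4.3 and the concomitant medication already recorded at visits. It overlaps with the primary endpoint and has the modest power shown above. The SAP would also have to say:
- which day's dose counts as the Week 10 dose;
- whether patients on budesonide alone belong to the stratum and how their dose is counted, since section 7.18 lists budesonide apart from GCS;
- how a missing Week 10 dose is handled, because non-responder imputation in section 9.9 gives no value for a dose change. One option is the last recorded dose, with a sensitivity analysis that assumes no reduction.

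No tapering or rescue rule changes.

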3.2.3. Safety Endpoints

- Incidence of AEs
- Incidence of SAEs
- Vital signs
- Electrocardiogram (ECG)
- Physical Examination
- Laboratory Findings

4. STUDY POPULATION

All relevant medical and non-medical conditions should be taken into consideration when deciding whether a particular patient is suitable to participate in this study. Patient eligibility should be reviewed and documented by an appropriately qualified member of the investigator's study team prior to inclusion in the study. If patient fails to fulfil the inclusion/exclusion criteria, patient can be considered to be re-screened at a later time if eligible.

4.1. Inclusion Criteria

Patients must meet all of the following inclusion criteria to be randomised in the study:

1. Male or female ≥ 18 years of age
2. Established diagnosis of UC, with minimum time from diagnosis of ≥ 3 months
3. Moderately to severely active left sided UC (disease should extend 15 cm or more above the anal verge and not beyond the splenic flexure) determined by

a Modified Mayo score (excluding the friability at grade 1 for the endoscopic sub score) of 6 to 12 with an endoscopic sub score ≥ 2 assessed by central reading of endoscopy performed at screening visit 1b, and no other individual sub score < 1

4. Current oral 5-ASA/SP use or a history of oral 5-ASA/SP use
5. Current GCS use or history of GCS dependency, refractory, or intolerance, including no GCS treatment due to earlier side-effects (only one of the GCS criteria have to be fulfilled, see definition in European Crohn's and Colitis organisation (ECCO) guidelines)
6. Demonstrated an inadequate response, loss of response, or intolerance to **at least one** of the following agents:
 - Immunomodulators, e.g. cyclosporine, methotrexate, AZA/6-MP, tacrolimus
 - For example, signs and symptoms of persistently active disease despite previous treatment with at least one 8 week regimen of oral AZA (≥ 1.5 mg/kg) or 6-MP (≥ 0.75 mg/kg) or lower doses prompted by intolerance or thiopurine methyltransferase (TPMT) deficiency *or*
 - For example, previous intolerance (including, but not limited to, nausea/vomiting, abdominal pain, pancreatitis, liver function test (LFT) abnormalities, lymphopenia, TPMT genetic mutation, infection) to at least one immunomodulator
 - TNF- α inhibitors and/or anti-integrins:
 - Signs and symptoms of persistently active disease despite previous treatment with at least one induction regimen with 2 doses at least 2 weeks apart (or doses as recommended according to the current labels) of for e.g.:
 - Infliximab 5 mg/kg (intravenous (IV)) *or*
 - Golimumab 200/100 mg (subcutaneous (SC)) *or*
 - Adalimumab 160/80 mg (SC) *or*
 - Vedolizumab 300 mg (IV) *or*
 - History of intolerance (including but not limited to infusion-related reaction, demyelination, congestive heart failure, infection)

Recurrence of symptoms during maintenance dosing with any of the above medications following prior clinical benefit, (secondary failure) [discontinuation despite clinical benefit does not qualify]

7. Allowed to receive a therapeutic dose of following UC drugs during the study:
 - a) Oral GCS therapy (≤ 20 mg prednisone or equivalent/daily) providing that the dose has been stable for 2 weeks prior to visit 1a
 - b) Oral MMX Budesonide therapy (9mg/daily) initiated at least 8 weeks before screening visit 1 a

- c) Oral 5-ASA/SP compounds, providing that the dose has been stable for 2 weeks prior to visit 1a and initiated at least 8 weeks before visit 1a
 - d) AZA/6-MP providing that the dose has been stable for 8 weeks prior to visit 1b and been initiated at least 3 months before visit 1a
8. Ability to understand the treatment, willingness to comply with all study requirements and ability to provide informed consent

4.2. Exclusion Criteria

Patients presenting with any of the following will not be included in the study:

1. Suspicion of differential diagnosis such as; Crohn's enterocolitis, ischaemic colitis, radiation colitis, indeterminate colitis, infectious colitis, diverticular disease, associated colitis, microscopic colitis, massive pseudopolyposis or non-passable stenosis
2. Acute fulminant UC and/or signs of systemic toxicity
3. UC limited to the rectum (disease which extend <15 cm above the anal verge)
4. History of malignancy, except for:
 - Treated (cured) basal cell or squamous cell in situ carcinoma
 - Treated (cured) cervical intraepithelial neoplasia or carcinoma in situ of the cervix with no evidence of recurrence within the previous 5 years prior to the screening visit 1a
5. History or presence of any clinically significant disorder that, in opinion of the investigator, could impact on patient's possibility to adhere to the protocol and protocol procedures or would confound the study result or compromise patient safety
6. Concomitant treatment with cyclosporine, methotrexate, tacrolimus, TNF- α inhibitors, anti-integrins or similar immunosuppressants and immunomodulators at enrolment. Any prior treatment with such drugs must have been discontinued at least 8 weeks prior to visit 1a *or* have non-measurable serum concentration levels
7. Treatment with rectal GCS, 5-ASA/SP or tacrolimus within 2 Weeks before visit 1b
8. Long term treatment with antibiotics or non-steroidal anti-inflammatory drugs (NSAIDs) within two weeks prior to visit 1a (one short treatment regime for antibiotics and occasional use of NSAIDS are allowed)
9. Serious active infection
10. Gastrointestinal infections including positive Clostridium difficile stool assay
11. Currently receiving parenteral nutrition or blood transfusions
12. Females who are lactating or have a positive serum pregnancy test during the screening period

13. Women of childbearing potential not using reliable contraceptive methods (reliable methods are barrier protection, hormonal contraception, intra-uterine device or abstinence) throughout the duration of the study
14. Concurrent participation in another clinical study with investigational therapy *or* previous use of investigational therapy within 5 half-lives and within at least 30 days after last treatment of the experimental product prior to enrolment
15. Previous exposure to cobitolimod

